**Objectives:**

Primary Objective: to reduce tinnitus loudness and life impact.  
Secondary Objectives: to alter the tinnitus spectrum minimum masking level

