## 3 OBJECTIVES AND ENDPOINTS

### 3.1 PRIMARY MEASURES

1) Tinnitus loudness: Measurements by the TinnTester software (McMaster University, supplied by [name]) are completed by interactive computer administered in a soundproof booth. To assess loudness in this procedure, subjects adjust the level of each of 11 sounds differing in center frequency to match the level of their tinnitus. This gives a measure of loudness in sound pressure level (SPL) for each subject (loudness matching method). The subjects then rate each sound for the similarity of its frequency to the frequency of their tinnitus. This gives the tinnitus frequency spectrum for each subject. Data are recorded automatically by the software. This software package has been used extensively by the tinnitus research community and is published (Roberts et al, 2008). The TinnTester sounds will be delivered by the devices through calibrated earphones. The devices have hardware limits on the sound pressure levels so that they are presented at safe levels (lower than 60 dB SL (above threshold).

2) Tinnitus Functional Index (TFI): The 25 item version of the TFI determines severity of tinnitus on a 100 point numeric scale (scores above 17 indicate the patient's tinnitus is a problem) based on patients' responses to 25 questions regarding the impact their tinnitus has on their emotional, social, and mental well-being. A thirteen-point reduction in score is considered clinically significant, indicating a noticeable improvement in tinnitus. This version has recently been validated for the test-retest reliability and internal consistency in New Zealand and the UK.

3) Tinnitus Handicap Inventory (THI): A 25 item questionnaire which assesses subjective impacts of tinnitus related to quality of life on a 100 point numeric scale. Scores 17 points or higher are considered bothersome tinnitus. We are including this measure as several other studies use it so it is a point of comparison.

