## 9 STATISTICAL CONSIDERATIONS

### 9.1 STATISTICAL HYPOTHESES

The data will be collected throughout the course of the study by blinded test administrators. A General Linear/Logistic Mixed (GLLM) effects analytic model was developed in consultation with UM statistics department prior to our preliminary trial. GLLM is considered ideal when analyzing repeated measures as it treats time as a continuous variable and can account for missing data. This framework can readily adapt to subgroupings present in the data. GLLM analysis includes random and fixed effects. In this study, treatment order (active first vs sham first), treatment condition (active, active washout, sham, sham washout), baseline loudness, baseline TFI, and interaction of treatment and treatment order are treated as fixed while intercept is treated as a random effect. All metrics are computed relative to baseline for each subject.

MICHR has provided templates, tools, and general guidance in support of activities conducted by the study team to facilitate study and data management, and will continue to do so. The University of Michigan's Department of Statistics Consulting for Statistics, Computing and Analytics Research (CSCAR) has provided individualized support and training to our team on management, collection, and analysis of data for phase 1 (which is identical to the second except in terms of subject numbers and treatment duration). Staff are available for continued support in the use of technical software, and advanced computing in research.

- Primary Efficacy Endpoint(s):
  - 1) Objective Tinnitus Loudness
  - 2) Tinnitus Functional Index
  - 3) Tinnitus Handicap Index
- Secondary Efficacy Endpoint(s):
  - 1) Tinnitus bandwidth/spectrum
  - 2) Minimum masking level
  - 3) Tinnitus Hearing Survey

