## 9.2 SAMPLE SIZE DETERMINATION

To compute statistical power, we utilized a linear model of our prior trial data, where change from baseline in both TFI and loudness is a linear function of the time in study, with a constant term reflecting enrollment in study. Time in study was extended out to six weeks. Data sample independence was achieved by normalizing each subject by their own baseline. With these parameters, alpha = 0.05 and beta = 0.8, we simulated new data sets with samples ranging from 5 to 50. Model slopes were tested for significant differences using analysis of covariance. Each new model was simulated 50 times, and the total number of significant models counted. The first sample size where the computed power was greater than 0.8 was determined. 14 subjects are required per arm to achieve a power of 0.8 for the loudness test, and 17 subjects are required per arm for the TFI. Thus, this study design requires a total subject count of 34. We propose a minimum sample size of 50 to account for subject variability and compliance.

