## 9.4 STATISTICAL ANALYSES

Data will be analyzed as means with standard deviations. All hypothesis-testing derived analyses will utilize an alpha of 0.05, beta of 0.8, and utilize two-tailed tests.

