### 9.4.1 ANALYSIS OF THE PRIMARY EFFICACY ENDPOINT(S)

For all endpoints (Tinnitus loudness, TFI and THI), the following approach will be utilized. All measures are ordinal, repeated measures. Final analysis will occur after unblinding.

Tinnitus loudness is measured by having subjects match the loudness and likeness of their tinnitus to one of 11 sounds with different center frequencies. Absolute differences are averaged relative to baseline to determine loudness. TFI and THI are questionnaires to be completed at each weekly visit. Both are measured on an interval scale. See section 3.1 for more details

A General Linear/Logistic Mixed (GLLM) effects analytic model will be used. GLLM is considered ideal when analyzing repeated measures as it treats time as a continuous variable and can account for missing data. This framework can readily adapt to subgroupings present in the data. GLLM analysis includes random and fixed effects. In this study, treatment order (active first vs sham first), treatment condition (active, active washout, sham, sham washout), baseline loudness, baseline TFI, and interaction of treatment and treatment order are treated as fixed while intercept is treated as a random effect.

Adjustments for Type I error over the set of endpoints is unnecessary as the measures are not directly related.

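### Section 9.4.1 rules out Type I error adjustment over three primary endpoints for an unsound reason, and no success rule is stated: if any one endpoint suffices, the false-positive risk is 14.3% under independence

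*Combined protocol and SAP*

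**What the plan says.** The synopsis, section 9.1 and section 9.4.1 each list three primary endpoints: loudness by TinnTester, TFI and THI. The third appears in 9.1 as "3) Tinnitus Handicap Index". Section 9.4.1 treats them alike: "For all endpoints (Tinnitus loudness, TFI and THI), the following approach will be utilized". Section 9.4 sets the level for every test: "All hypothesis-testing derived analyses will utilize an alpha of 0.05, beta of 0.8, and utilize two-tailed tests" (I read the beta as power).

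Section 9.4.1 closes with "Adjustments for Type I error over the set of endpoints is unnecessary as the measures are not directly related". This is current text, not a remnant in the amendment log.

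On what counts as success, the nearest statement is the synopsis objective: "Primary Objective: to reduce tinnitus loudness and life impact". It joins loudness and life impact, but it is an objective and not a decision rule. The mixed model in 9.4.1 has a treatment factor with four levels (active, active washout, sham, sham washout) and its interaction with treatment order. No contrast is singled out as the test of an endpoint.

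**The concern.** Adjustment is needed, or not, according to how the endpoints combine into a conclusion. Whether the measures are related does not settle that. If any one significant endpoint makes the trial positive, unrelated measures provide three nearly separate chances of a false positive, so the reason given in 9.4.1 argues for adjustment. If all three must succeed, no adjustment is needed whatever the correlation. If each endpoint supports its own separate claim, 5% per endpoint can be defended, but the plan would have to say so.

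Because none of these is declared, one p-value below 0.05 among three could be presented as a positive trial, and a reader could not tell whether that was planned. Section 9.4.1 places the final analysis after unblinding, so a rule chosen at that stage would come too late.

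The missing contrast makes this worse. Section 3 lists four assessment times per endpoint, and section 9.3 plans both intention-to-treat and per-protocol analyses without naming one as primary. Any alpha rule presupposes one identified test per endpoint.

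**Working it through.** **Inputs.** Three primary endpoints (9.1, 9.4.1); two-sided 0.05 per test (9.4); no adjustment (9.4.1); 14 per arm for loudness and 17 for TFI at power 0.8, and a minimum of 50 subjects (9.2). The documents give no correlations between endpoints, so every correlation below is an assumption.

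**The plan's own figures.** It states no overall error rate to reproduce. The total of 34 in 9.2 is 2 × 17. The 14 and 17 cannot be re-derived, because they come from simulated slopes whose values and variances are not given.

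**Any one of three, independent, one test each.** 1 − (1 − 0.05)³ = 1 − 0.857375 = 0.1426, or 14.3%. The bound under any dependence is 3 × 0.05 = 15%. These rates count rejections in either direction, as the two-sided 5% does.

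**Any one of three, common correlation r.** Write each test statistic as √r·U + √(1−r)·eᵢ with U and eᵢ independent standard normal. The probability of at least one rejection is 1 − ∫ φ(u)[Φ((c − √r·u)/√(1−r)) − Φ((−c − √r·u)/√(1−r))]³ du. Take c = 1.960 for 0.05 per test and c = 2.394 for 0.05/3 = 0.0167, which is Holm's first step. Under the global null, Holm makes some rejection exactly when its first step does.

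| r (assumed) | Unadjusted | Holm |
|---|---|---|
| 0 | 14.3% | 4.9% |
| 0.3 | 13.6% | 4.8% |
| 0.5 | 12.5% | 4.5% |
| 0.8 | 9.8% | 3.5% |
| 0.9 | 8.4% | 3.0% |

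A mixed case, with correlation 0.8 between TFI and THI and 0.3 between loudness and each, gives 12.1% unadjusted (simulation, 2,000,000 draws). The unadjusted rate falls as correlation rises, which is the opposite of what 9.4.1 implies, and it exceeds 5% in every case shown. These figures are not ceilings if more than one contrast is tested per endpoint.

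**All three required.** The chance of a false overall claim is at most 5%, because at least one endpoint without an effect would have to be rejected at 0.05.

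**Power cost of Holm, illustration only.** Section 9.2 says "14 subjects are required per arm to achieve a power of 0.8 for the loudness test". For the questionnaire endpoint that it powers, it gives a separate figure: "17 subjects are required per arm for the TFI". Take these at face value as exact 80% points of a two-sample comparison with 25 per arm (50/2). Power is then Φ(2.802·√(25/n₀) − z), where 2.802 = 1.960 + 0.842.
- Loudness, n₀ = 14: 2.802 × 1.336 = 3.744. Power is Φ(1.784) = 96% at 0.05 and Φ(1.350) = 91% at 0.0167.
- TFI, n₀ = 17: 2.802 × 1.213 = 3.398. Power is Φ(1.438) = 92% at 0.05 and Φ(1.004) = 84% at 0.0167.

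The design is a crossover and 9.2 tested slopes, so these show only the order of magnitude. Power for THI cannot be computed, because 9.2 does not cover it.

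**The case against.** The best reply is that the sponsor intended separate claims. The table in section 3 lists loudness, TFI and THI as three numbered primary objectives, each with its own justification, and the sentence in 9.4.1 could be a clumsy way of saying that each stands alone at 5%. That reading is possible, but the table declares no claims. It also gives TFI and THI the same justification, which sits badly with calling the measures unrelated.

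A second reply is that 14.3% uses an implausible correlation. TFI and THI are both 25-item, 100-point questionnaires on tinnitus impact and are unlikely to be independent. That is fair: 14.3% is the independence case, not an estimate for this trial. The mixed case still gives 12.1%.

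Third, sections 7.1 and 8.2 call TFI and TinnTester the primary outcome measures, and 9.2 powers only those two. That wording sits in a rule for discontinuing a participant, while the synopsis, 9.1 and 9.4.1 list three. With two endpoints the any-one rate would still be 1 − 0.95² = 9.75%.

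Fourth, the power illustration rests on 50 simulations per model, with a standard error of √(0.8 × 0.2/50) = 5.7 percentage points at 0.8. If true power at 17 per arm were 70%, the TFI figures would be about 85% and 73%. This stands as a caution on the power figures, but it does not touch the error rates.

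Finally, this is a Phase I/II trial and the defect can be cured by wording. Both are true. But section 6.1.1 anticipates FDA review after completion, and the wording can repair the defect only if it is fixed before unblinding.

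**Conclusion.** The concern holds. The justification in 9.4.1 is wrong as written, and the plan has no success rule. If any one endpoint suffices, with one two-sided 0.05 test each, the overall false-positive rate is 14.3% under independence, and 13.6% to 8.4% at assumed common correlations of 0.3 to 0.9. If all three must succeed it is at most 5%. The inflation therefore depends on a rule that the plan does not state. The unsound reason and the missing rule do not depend on the sponsor's intent. This must be fixed before unblinding.

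**What to change.** Before unblinding, revise 9.4.1 as follows.

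1. Delete the sentence on Type I error adjustment.
2. Name the one active-versus-sham contrast from the mixed model that decides each endpoint.
3. State the success rule. If any one endpoint suffices, control overall two-sided alpha at 0.05 either with Holm or with a fixed sequence whose full order is given. Loudness, TFI, THI follows the order already listed in the synopsis and 9.1. Placing THI last is reasonable, since section 3.1 says of it: "We are including this measure as several other studies use it so it is a point of comparison". Alternatively, state that all three must succeed.

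If separate claims per endpoint are intended, the success rule must say so, and no overall claim may then rest on a single significant endpoint.

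The change is to wording only. On the illustrative figures, testing at Holm's first-step level lowers power from about 96% to 91% for loudness and from 92% to 84% for TFI. Holm's own power per endpoint is at least as high as at that level. A fixed sequence keeps 0.05 at each step but blocks later claims once an endpoint fails. Requiring all three costs joint power, by an amount that cannot be computed until 9.2 covers THI.

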### 9.4.2 ANALYSIS OF THE SECONDARY ENDPOINT(S)

The following analytical framework will be applied to 2ndary measures (see section 3.2 for more details). Analyses are not dependent on primary-measures. All measures are ordinal, repeated measures. Data will be analyzed using repeated-measures ANOVA, and shown as mean+/-SEM. Normality will be assessed using Kolmogorov-Smirnoff tests, and non-parametric tests used for non-normally distributed data. To assess how the secondary measures might co vary with the primary measures, we will use principal component analysis or linear fixed effects models.

Non-compliant and missing data points will be excluded from analysis.

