### 3.2 SECONDARY MEASURES

1) Tinnitus bandwidth/spectrum: Near its start the TinnTester software asks subjects to indicate which of three sounds best resembles their tinnitus; 5 kHz pure tone ("tonal" tinnitus), a narrow band noise centered at 5 kHz ( $\pm 5\%$  of CF, BPN5 masker, "ringing" tinnitus), or a wider band of noise centered at 5 kHz ( $\pm 15\%$  of CF, BPN15 masker, "hissing" tinnitus). We will relate treatment outcomes to tinnitus bandwidth by these measurements. We will also be able to determine whether the treatment alters bandwidth.

2) Minimum Masking Level (MML): Subjects adjust the level of the 5 kHz BPN15 sound until they can no longer hear their tinnitus. MML may prove sensitive to the bimodal treatment procedure. MML should be reduced, if tinnitus assessed by loudness matching is also reduced. However, even when tinnitus loudness is reduced, there are subjects for whom tinnitus cannot be masked.

3) Tinnitus Hearing Survey: A brief nine question survey which determines self-perceived handicap due to tinnitus, hearing loss, and hyperacusis. This questionnaire differs from the two primary questionnaires in that it qualifies any perceived handicap due to hearing loss and/or sound sensitivity (hyperacusis).

OBJECTIVES	ENDPOINTS	JUSTIFICATION FOR ENDPOINTS
Primary		
1) Objective Tinnitus loudness (TinnTester)	1) End of 1 st arm 2) End of first washout 3) End of 2 nd arm 4) End of second washout	To determine how use of device affects objective tinnitus loudness before and after the treatment and sham arms of the study.
2) Tinnitus Functional Index	1) End of 1 st arm 2) End of first washout 3) End of 2 nd arm 4) End of second washout	To determine how use of device affects the tinnitus and quality of life before and after the treatment and sham arms of the study
3) Tinnitus Handicap Index	1) End of 1 st arm 2) End of first washout 3) End of 2 nd arm 4) End of second washout	To determine how use of device affects the tinnitus and quality of life before and after the treatment and sham arms of the study
Secondary		
1) Tinnitus bandwidth/spectrum (TinnTester)	1) End of 1 st arm 2) End of first washout 3) End of 2 nd arm 4) End of second washout	To determine how use of the device may or may not change the perceived frequency (spectra) of tinnitus following the treatment or sham arms.

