## 9.3 POPULATIONS FOR ANALYSES

All subject's data will be analyzed in one cohort. We will perform both per-protocol and intention-to-treat analyses. While intention-to-treat analysis is ideal, our protocol may require subjects to adhere to a strict schedule in order to fully realize the benefit of the treatment. Our pilot study had excellent compliance rates, but a longer and larger study provides more opportunity for non-compliant subjects. Should sensitivity analysis between the intention-to-treat and per-protocol analyses attain significance, differences between compliant and non-compliant subjects will be further explored in an effort more fully understand who best can benefit from the bimodal protocol. Missing data and losses to follow-up will be managed using

a last observation carried forward approach. Sensitivity analysis to outliers will also be performed. If results differ significantly between with and without outliers, outliers will be further investigated to determine what factors impact the likelihood of a subject responding or being resistant to the treatment protocol.

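### Minimum masking level has no score for tinnitus that cannot be masked; if such results count as missing, a known worst outcome is discarded

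*Combined protocol and SAP*

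**What the plan says.** - **How MML is obtained (section 3.2).** "Subjects adjust the level of the 5 kHz BPN15 sound until they can no longer hear their tinnitus". A subject who never reaches that point produces no level.
- **Such subjects are expected (section 3.2).** "However, even when tinnitus loudness is reduced, there are subjects for whom tinnitus cannot be masked".
- **Expected direction (section 3.2).** "MML should be reduced, if tinnitus assessed by loudness matching is also reduced". The objectives table makes reduction under active treatment the question for this endpoint.
- **Output limit (section 3.1).** TinnTester sounds are "presented at safe levels (lower than 60 dB SL (above threshold"). No maximum level is given for the MML test itself.
- **Analysis (section 9.4.2).** Repeated-measures ANOVA with means and standard errors, non-parametric tests if the data are not normal, and "Non-compliant and missing data points will be excluded from analysis".
- **General missing-data rule (section 9.3).** "a last observation carried forward approach".

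No section gives a code, score, censoring rule or rank for a result of 'not maskable'.

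**The concern.** A subject who still hears the tinnitus at the loudest permitted sound has an MML above that level. That is the worst result on the scale, not an unknown one. The plan anticipates the result, gives it no number, and excludes missing points in the section that governs this endpoint. The natural outcome is that it is left blank and dropped.

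Two things are then at stake. First, a subject who is unmaskable under sham and maskable under active has responded on this measure, yet contributes nothing to a paired comparison. Second, if treatment lowers MML, unmaskable results will be commoner under sham, so exclusion removes high values mainly from the comparator.

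The rule in section 9.3 does not solve this. A subject who becomes unmaskable would keep an earlier, lower level. The two sections also disagree on what happens to a missing secondary value.

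**Working it through.** The plan gives no MML mean, SD, effect size, ceiling or unmaskable share. Its sample size (2 x 17 = 34 required, minimum 50 proposed) comes from loudness and the Tinnitus Functional Index, so there is no MML figure to reproduce. **All inputs below are assumptions** that show the mechanism and a range.

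**Set A.** Latent MML is normal with mean 55 dB under sham, between-subject SD 18 and within-subject SD 6. The total SD is √(18² + 6²) = √360 = 18.97, and the active-sham correlation is 324/360 = 0.90. A result is unmaskable if it exceeds a ceiling of 75 or 65 dB.

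Unmaskable share = 1 − Φ((ceiling − mean)/18.97):
- Sham: 1 − Φ(20/18.97) = 0.146; 1 − Φ(10/18.97) = 0.299.
- Active, true effect −6 dB: 1 − Φ(26/18.97) = 0.085; 1 − Φ(16/18.97) = 0.200.

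Simulated results for a true effect of −6 dB:

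| | ceiling 75 | ceiling 65 |
|---|---|---|
| Unmaskable on sham only | 7.3% | 12.0% |
| Unmaskable on active only | 1.2% | 2.0% |
| Active − sham, complete pairs | −5.7 dB | −5.45 dB |
| Shrinkage, (6 − estimate)/6 | 5% | 9% |
| Complete pairs with baseline also measurable | −5.78 dB (4%) | −5.60 dB (7%) |

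For a true effect of −4 dB with 50 subjects, complete pairs make up 0.835 and 0.670 of subjects, so 50 x 0.835 = 42 and 50 x 0.670 = 33.5 are expected. Two-sided power at 0.05:

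| | ceiling 75 | ceiling 65 |
|---|---|---|
| Paired t-test, complete pairs | 0.83 | 0.71 |
| Signed-rank, unmaskable ranked worst | 0.85 to 0.87 | 0.80 |

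At −6 dB, complete-pair power is 0.99 and 0.97, so little is lost.

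**Set B.** SD 12, true effect −6 dB, 50 subjects, and 10%, 20% or 30% unmaskable under sham:
- Correlation 0.5: complete pairs give −5.4, −4.8 and −4.5 dB, a shrinkage of 10%, 20% and 25%. Power falls from about 0.93 to 0.87, 0.76 and 0.65.
- Correlation 0.8: −5.7, −5.4 and −5.2 dB, a shrinkage of 5%, 10% and 13%.

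**Where there is no bias (SD 12):**
- True effect 0: the estimate stays near 0 and the type I error near 0.05.
- The same subjects unmaskable in both conditions whatever the treatment: the estimate among the rest is −6.0 dB. Only numbers fall, with power about 0.92, 0.87 and 0.83 at 10%, 20% and 30%.

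**Ceiling substitution.** Entering the maximum level and comparing means is not a clean repair. In set B at correlation 0.5 and 20% unmaskable, it restores power to 0.90 but gives −5.1 dB. In the always-unmaskable case it gives −5.4, −4.8 and −4.2 dB.

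**The case against.** Four arguments can be made against the point.

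1. **Coding as missing is an inference.** A reader might conclude that the plan does exclude unmaskable subjects. No section says so. A site could record the top level or a note instead, and section 9.3 names a different missing-data rule. This stands: the documented defect is the absence of a scoring rule, and exclusion is its likeliest consequence.
2. **Differential loss is conditional.** A reader might infer that exclusion must remove more sham than active values. Section 3.2 says that "even when tinnitus loudness is reduced, there are subjects for whom tinnitus cannot be masked", which fits unmaskability that persists despite response. In that case the contrast is unbiased among the rest. Likewise, a subject unmaskable at baseline has no change score in either condition. This stands too.
3. **The effect could look much larger.** Averaging whatever points remain in each condition, with different subjects in each mean, set A gives about −4.15 and −3.2 dB for a true −6, a shrinkage of 31% and 47%. That does not fit the design: this is a crossover in which all subjects receive both conditions, analysed by repeated measures relative to each subject's baseline. The within-subject figure in set A is 5-9%.
4. **The non-parametric option in 9.4.2 may suffice.** It helps only if the result is recorded. A value already excluded cannot be ranked.

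**Conclusion.** The gap is real but minor. The plan predicts an outcome that has no number, assigns it no score, and has two conflicting rules for missing values. If unmaskable results are treated as missing and excluded, the plan discards known worst outcomes and some responders.

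Attenuation of the within-subject effect follows only if unmaskability tracks a high MML and active treatment lowers MML. It is then modest: about 5-9% in set A, and up to about 25% in set B at correlation 0.5 with 30% unmaskable under sham. The more dependable cost is lost subjects and, for smaller effects, lost power. A claim that the rule as written removes a third to a half of the effect is not supported.

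Any bias from exclusion is towards no effect, so it does not create a false claim of benefit, and only one of three secondary endpoints is affected. Every size quoted rests on assumed inputs.

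**What to change.** Make these changes before unblinding, so that the choice cannot depend on results:

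- State the maximum MML test level in section 3.2.
- Record 'not maskable at maximum level' as an outcome with its own code, distinct from a missed or failed test.
- In section 9.4.2, analyse MML with unmaskable ranked above every measured level (a signed-rank type of comparison), or as right-censored at the maximum in a mixed model. Ranking is the safer choice if some subjects are unmaskable at any level, because the censored model assumes that they lie in the upper tail of the same distribution.
- Report the number unmaskable by condition and visit.
- Reconcile sections 9.3 and 9.4.2 on truly missing secondary values.

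The cost is one code on the form and a few sentences. The downside is that a rank or censored result is slightly harder to express in dB; the measured levels and unmaskable counts can be tabulated alongside it.
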